5.9 Receiving, Storage, Dispensing and Return

5.9.1 Receipt of Drug Supplies

The magnesium sulfate and normal saline are already available for use in the anesthesia drug carts.

5.9.2 Storage

The drugs are maintained at room temperature with no particular light protection requirements in every anesthesia drug cart. The special handling requirements are necessary.

5.9.3 Dispensing of Study Drug

The anesthesia team will follow instructions provided to them to prepare the study drug, using multiple vials of the drug already available for use in the anesthesia drug cart.

CONFIDENTIAL

This document is confidential and the property of Stanford University School of Medicine.

5.9.4 Return or Destruction of Study Drug

By the completion of the anesthetic, the drug's bolus and infusion will be documented in the electronic anesthetic record. The unused study drug remaining in the syringe will be wasted and destroyed.

6 Study Procedures

6.1 24 to 72 hours prior to scheduled surgery

- 6.1.1 Patients undergoing per-oral endoscopic myotomy (POEM) in the SHC operating rooms will be identified, and screened by phone whether or not they agree to the study.

6.2 Day of surgery

- 6.2.1 In the preoperative holding area, all enrolled patients will have preoperative plasma calcium and magnesium levels drawn and complete the esophageal symptoms questionnaire (ESQ), a validated survey to assess symptoms of dysphagia, globus, and reflux.

6.2.2 The patient will proceed to the OR for anesthetic care.

- 6.2.2.1 Patients will undergo rapid sequence induction of general anesthesia. In the control group, the anesthesia team will use ketamine, propofol, succinylcholine, and esmolol and/or opioids at their discretion. In the treatment arm, the anesthesia team will use ketamine and propofol using lean body weight (LBW) dosing, and succinylcholine at total body weight (TBW) dosing. After endotracheal tube placement and confirmation, sevoflurane in air and oxygen will be used for maintenance of general anesthesia. The anesthesiologist will ensure adequate neuromuscular relaxation throughout the case.

- 6.2.2.2 In the treatment arm, the anesthesia team will prepare a magnesium sulfate infusion within a 20 ml syringe. Patients will receive a magnesium sulfate bolus of 50 mg/kg lean body weight over 15 minutes, followed by a magnesium sulfate infusion at 25 mg/kg/hr when the endoscopist begins mucosal incision. In addition, the patients will receive dexamethasone 0.1-0.2 mg/kg at the start of case, and ondansetron 4 mg at the end of case. The magnesium infusion will be discontinued at extubation. After surgery, patients will be admitted to the postanesthesia care unit. For mild pain reported as a numeric score ranging from 1 to 3, acetaminophen 1000 mg IV will be offered. For pain greater than a score of 3, opioids (fentanyl and hydromorphone) will be available. For nausea and vomiting, prochlorperazine and haloperidol will be provided. Calcium gluconate and a code cart with emergency drugs and airway equipment will be made available in case of symptoms concerning for magnesium toxicity.

- 6.2.2.3 In the control arm, the anesthesia team will prepare a normal saline infusion within a 20 ml syringe. Patients will receive a normal saline bolus of 50 mg/kg lean body weight over 15 minutes, followed by a normal saline infusion at 25 mg/kg/hr when the endoscopist begins mucosal incision. Opioids (fentanyl and hydromorphone) will be administered for analgesia at the discretion of the anesthesia team. In addition, patients

CONFIDENTIAL

This document is confidential and the property of Stanford University School of Medicine.

will receive dexamethasone and ondansetron in the aforementioned doses. After surgery, patients will be admitted to the postanesthesia care unit, where opioids (fentanyl and hydromorphone) and antiemetics (anesthesia team's discretion) will be available for further pain and nausea management.

6.3 All study participants will repeat the ESQ in the PACU when the nursing team deems the patient's recovery appropriate enough to participate.

6.4 Postoperative Day 1

6.4.1 The ESQ and serum calcium/magnesium levels will be reobtained in the morning of POD1.

7 Statistical Plan

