5.4 Preparation and Administration of Study Drug

The anesthesia team will prepare the study treatment based on the instructions within the envelope. Specifically, the anesthesia team will be instructed to draw up 10 g (20 ml) of the study drug within a 20 ml syringe, or to draw up 20 ml of normal saline within a 20 ml syringe. Although both medications are colorless and transparent, and thus are indistinguishable to the endoscopist, the syringes will be labeled as “study” to minimize drug error during the intraoperative anesthetic management. These medications will be administered using a syringe pump (Alaris; Becton, Dickinson and Company, New Jersey, USA) available in all SHC operating rooms. Instructions to manually program the syringe pump will be provided.

Specifically, the anesthesia team will be instructed to enter 10 g of the study drug in 20 ml of volume, and to enter the patient’s lean body weight. The team will enter the infusion rate as 25 mg/kg/hr, and save these settings.

When the endoscopist announces that she/he will start the mucosal incision, the syringe pump will be programmed to bolus 50 mg/kg over 15 minutes. After the bolus is administered, the syringe pump will default to the infusion rate of 25 mg/kg/hr. The anesthesia team will stop the infusion at extubation.

CONFIDENTIAL

This document is confidential and the property of Stanford University School of Medicine.

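### The two arms have different written rules for opioids, recovery-room analgesia and antiemetics, so part of any opioid-use difference may come from the rules and not from magnesium

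*Combined protocol and SAP*

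**What the plan says.** Section 6.2.2 of the protocol gives each arm its own care text.

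- **Induction (6.2.2.1).** Control: "In the control group, the anesthesia team will use ketamine, propofol, succinylcholine, and esmolol and/or opioids at their discretion". Magnesium: "In the treatment arm, the anesthesia team will use ketamine and propofol using lean body weight (LBW) dosing", plus succinylcholine by total body weight. No opioid or esmolol is named for magnesium.
- **During surgery.** Control (6.2.2.3): "Opioids (fentanyl and hydromorphone) will be administered for analgesia at the discretion of the anesthesia team". Section 6.2.2.2, for magnesium, has no corresponding sentence.
- **Recovery-room analgesia.** Magnesium (6.2.2.2): "For mild pain reported as a numeric score ranging from 1 to 3, acetaminophen 1000 mg IV will be offered", then "For pain greater than a score of 3, opioids (fentanyl and hydromorphone) will be available". Control (6.2.2.3) describes a unit "where opioids (fentanyl and hydromorphone) and antiemetics" are available, with no pain-score threshold and no acetaminophen step.
- **Recovery-room antiemetics.** Magnesium: "For nausea and vomiting, prochlorperazine and haloperidol will be provided". Control: at the anesthesia team's discretion.

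Dexamethasone and ondansetron are expressly the same in both arms. Section 5.6, which is not arm-specific, expects standard anesthetic care for all patients, with narcotics among the drugs given as needed at the team's discretion.

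On who knows the allocation, section 5.4 says: "The anesthesia team will prepare the study treatment based on the instructions within the envelope". Section 5.8 names only the endoscopist and the patient as blinded.

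The Study Summary makes lower perioperative opioid requirements part of the hypothesis. Section 3.3 lists intraoperative opioid use, postoperative consumption and discharge prescription as secondary endpoints. Section 7.2 compares them by chi-square or Fisher's exact test, with Mann-Whitney for continuous variables.

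**The concern.** A placebo-controlled comparison attributes a difference to the drug because everything else is handled alike. Here the written care also differs by assigned arm, and it differs in the thing being measured: when an opioid is given. Randomisation cannot remove a difference that is itself assigned with treatment, and section 7.2 has no analysis that would separate the two sources. A larger sample would only estimate the combined effect more precisely.

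Blinding gives little protection during surgery, because the team applying the discretionary rules has opened the envelope.

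The pain outcomes, including the primary, may be affected too, but the degree and direction are unknown. The plan does not define 0 h relative to rescue dosing, and the two arms' analgesics could move pain scores either way.

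**Working it through.** **Step 1. Follow a patient through the two texts.**

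| Situation | Magnesium text | Control text |
|---|---|---|
| Induction | no opioid or esmolol named | esmolol and/or opioids, discretionary |
| Intraoperative analgesia | silent on opioids | fentanyl and hydromorphone, discretionary |
| Recovery room, score 2 | IV acetaminophen | opioids available; no acetaminophen step |
| Recovery room, score 5 | opioids available | opioids available |

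Section 5.6 closes the first two rows if the team follows it in preference to 6.2.2. It does not touch the third row, because it contains no pain-score threshold and no acetaminophen rule. If the arm texts are followed, the first three rows all push towards less opioid use on magnesium, whatever magnesium does.

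**Step 2. How large a rule-driven gap matters.**

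Inputs from the plan: two-sided alpha 0.05 (7.2), and 50 per arm (7.1, where 45/(1 − 0.10) = 50). The plan's sample size is set for the primary pain outcome and is used here only for the group size.

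Assumed, because the documents give no opioid-use rates: magnesium has no effect; the proportion of control patients given any opioid, p, is 0.70, 0.80 or 0.90; and the rules lower it by a gap g in the magnesium arm.

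Formula: with x₁ and x₂ patients given an opioid out of n = 50 per arm, the uncorrected chi-square test rejects when |x₁ − x₂|/n > 1.96 × √(2p̄(1 − p̄)/n), where p̄ = (x₁ + x₂)/(2n). The chance of a significant result is the sum of Bin(x₁; 50, p) × Bin(x₂; 50, p − g) over all rejecting pairs. Fisher's test uses the same sum with its own rejection region.

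Hand check at 80% against 70%: p̄ = 0.75, the null standard error is √(2 × 0.75 × 0.25/50) = 0.0866, and the actual standard error is √((0.16 + 0.21)/50) = 0.0860. The chance is about Φ((0.10 − 1.96 × 0.0866)/0.0860) = Φ(−0.81) = 0.21. The exact sum gives 0.212.

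Exact results, chi-square / Fisher:

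| Gap (points) | Control 90% | Control 80% | Control 70% |
|---|---|---|---|
| 0 | 0.051 / 0.018 | 0.052 / 0.028 | 0.050 / 0.031 |
| 5 | 0.123 / 0.061 | 0.093 / 0.059 | 0.082 / 0.055 |
| 10 | 0.303 / 0.195 | 0.212 / 0.155 | 0.180 / 0.132 |
| 20 | 0.734 / 0.640 | 0.595 / 0.515 | 0.546 / 0.463 |
| 30 | 0.954 / 0.927 | 0.895 / 0.853 | 0.876 / 0.829 |

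**Step 3. Consumption as a continuous variable.** For Mann-Whitney with 50 per arm, 20,000 simulated trials with normal data (or log-normal data with the shift on the log scale) give these rejection rates for a rule-driven shift: 0 SD, 5%; 0.2 SD, 16%; 0.3 SD, 30%; 0.5 SD, 68%.

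**Step 4. Sensitivity to dropout.** With the 45 per arm that the plan expects to remain, the chi-square range is 17% to 28% at 10 points and 49% to 69% at 20 points, so the reading is unchanged.

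**The case against.** The strongest reply is section 5.6. It expects narcotics as needed for all patients, and 6.2.2.2 does not forbid them. The rest of the plan also presupposes that magnesium patients can receive opioids: it aims to reduce intraoperative use and plans a subgroup analysis by it. On this reading the intraoperative difference is loose drafting. That stands in part, since magnesium patients are not barred from opioids. But 6.2.2 is the step-by-step instruction, section 1.2 presents magnesium in the setting of opioid-free anesthesia, and a team could reasonably follow either section.

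Second, the recovery-room difference is narrow. Opioids are available and not mandated in both arms, the rules coincide above a score of 3, and acetaminophen is not prohibited in control. So the written ladder separates the arms only for patients scoring 1 to 3. This is correct, and the documents do not say how many patients that is. Still, the expressly matched dexamethasone and ondansetron show that the authors carried a rule across arms when they meant to, so the missing control ladder cannot be assumed to be shorthand.

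Third, the gaps in the calculation are assumed, and nothing in the documents favours 20 points over 5. This stands. The figures show what a given gap would do, not what this trial will see.

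Fourth, the quantified harm falls on secondary endpoints. This also stands, and no figure is offered for the primary outcome. The antiemetic difference, the attachment list and the subgroup item are side issues, and the conclusion does not depend on them.

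**Conclusion.** The concern holds and should be fixed before patients are treated under these texts. The care rules differ by arm as written, they act directly on the opioid endpoints, and the intraoperative ones are applied by a team that knows the allocation. A trial run this way compares two care packages and cannot assign an opioid difference to magnesium alone.

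Confidence is high that the texts differ and low on how large the resulting bias would be. Under the stated assumptions, a rule-driven gap of 5 points is close to harmless (Fisher 5% to 6%, chi-square 8% to 12%). A gap of 10 points or more is clearly harmful (Fisher 13% to 19%, chi-square 18% to 30% at 10 points). For the pain outcomes the concern is qualitative only.

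**What to change.** Reconcile sections 5.6 and 6.2.2.1 to 6.2.2.3 into one anesthetic, opioid, recovery-room analgesic and antiemetic rule, worded identically for both arms, so that only the content of the study syringe differs. In particular:

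- Apply the existing pain-score ladder to both arms.
- Have the clinical team write common triggers for intraoperative opioid and esmolol dosing in place of open discretion.
- Make any procedure attachment common to both arms; section 15 lists one for the magnesium group only.
- As a minor point, drop intraoperative opioid usage from the subgroup list in 7.2. It arises after randomisation and is one of the trial's own outcomes, so it should be kept as an outcome only.

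The cost is amendment wording, one common order set and slightly less clinical discretion, with no extra patients or procedures. The anesthesia team would still know the allocation, so bias falls only as far as written criteria replace discretion.

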3.2 Primary Study Endpoints

This study will evaluate the efficacy of magnesium sulfate on decreasing esophageal spasm-associated pain as measured by subjective pain scores and the esophageal symptoms questionnaire score.

CONFIDENTIAL

This document is confidential and the property of Stanford University School of Medicine.

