7.2 Statistical Methods

Data will be expressed as means \pm SD, number (proportion), relative risk, 95% CI, absolute risk reduction, or number needed to treat.

The primary outcome is the incidence of esophageal spasm-related pain at 0 h postoperatively, compared using the chi-square test.

The secondary outcomes of the incidence of esophageal spasm-related pain at 24 hours postoperatively, intraoperative opioid usage, postoperative opioid consumption, and discharge opioid prescription will be compared using the chi-square test or Fisher's exact test as appropriate. Continuous variables will be compared using the Mann–Whitney *U* test. Categorical variables will be compared using the chi-square test or Fisher's exact test as appropriate.

Post hoc subgroup analyses will be conducted regarding the incidence of esophageal spasm-related pain according to achalasia type (e.g. type 1, 2, or 3), preoperative H2-receptor antagonist use, preoperative proton pump inhibitor use, and intraoperative opioid usage. *Post hoc* subgroup analysis will be further conducted on postoperative magnesium levels and the incidence of esophageal spasm-related pain at 24 hours.

All *P* values will be two-sided, and a value of $P < 0.05$ will be considered statistically significant.

Comparisons of postoperative pain between the two groups at time 0 h and time 24 h will be analyzed using the Mann–Whitney *U* test and performed using an adjusted significance level of 0.0125 (0.05/4) after *post hoc* analysis using the Bonferroni method.

Statistical analyses will be performed using R version 4.0.3.

CONFIDENTIAL

This document is confidential and the property of Stanford University School of Medicine.

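### No reading is tied to the 0 h primary outcome, and the only scheduled PACU self-report can follow analgesia, so spasm pain treated earlier can be missed

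*Combined protocol and SAP*

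**What the plan says.** - Section 7.2: "The primary outcome is the incidence of esophageal spasm-related pain at 0 h postoperatively, compared using the chi-square test". Nothing defines 0 h, sets a window around it, gives a cut-off for pain present or absent, or names the reading that supplies it.
- Section 3.2 says the primary effect is assessed "as measured by subjective pain scores and the esophageal symptoms questionnaire score". No time is scheduled for the pain scores.
- Section 6.3: "All study participants will repeat the ESQ in the PACU when the nursing team deems" them recovered enough to take part. This is the only self-report scheduled on the day of surgery after the operation. The next is on the morning of postoperative day 1 (6.4.1).
- Section 6.2.1 describes the ESQ as "a validated survey to assess symptoms of dysphagia, globus, and reflux". Pain is not in that list.
- Section 6.2.2.2, magnesium arm, in the PACU: "For mild pain reported as a numeric score ranging from 1 to 3, acetaminophen 1000 mg IV will be offered", and "For pain greater than a score of 3, opioids (fentanyl and hydromorphone) will be available".
- Section 6.2.2.3, control arm: opioids are available in the PACU, and no score rule is written.
- No section requires a pain reading before the first PACU analgesic, or says how pain treated before an assessment is classified.

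**The concern.** A binary outcome at 0 h needs a reading at 0 h. The plan fixes only one PACU self-report, and its time depends on how the patient recovers. Analgesia can come first. A patient who wakes with spasm pain, is treated and is comfortable by the time of the questionnaire could be counted as having no event.

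This problem would remain even if the PACU rescue text were identical in both arms and the definition of spasm pain were agreed, because it comes from the order of rescue and observation. Analysis by intention to treat (7.3) cannot recover an event that was never recorded, and the 24 h outcome does not replace the primary one.

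**Working it through.** **Inputs.** From 7.1: control incidence 60%, a decrease of 30%, two-sided alpha 0.05, beta 0.20, 45 per group, 50 after 10% dropout. From 5.3: allocation 1:1. From 7.2: chi-square test. Assumed, because the documents give no value: r, the share of true events cleared by treatment before the reading and then counted as absent.

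**The plan's own figure.** With 60% vs 30% (absolute reading), the simple pooled formula is

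n = 2 p̄(1 − p̄)(1.960 + 0.842)² / d² = 2 × 0.45 × 0.55 × 7.849 / 0.09 = 43.2, so 44 per group.

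The stated 45 is close to this, and 45 / 0.90 = 50. The relative reading (60% to 42%) gives 2 × 0.51 × 0.49 × 7.849 / 0.0324 = 121.1, so 122 per group, which does not fit. The sample size is not in dispute; the absolute reading is used below.

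**Method.** Observed incidence in an arm = true incidence × (1 − r). Power is the sum of Bin(x; n, p₁) × Bin(y; n, p₂) over all x, y for which the uncorrected statistic 2n(x − y)² / [(x + y)(2n − x − y)] exceeds 3.841.

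| Cleared: control / magnesium | Observed: control vs magnesium | n = 45 per arm | n = 50 per arm |
|---|---|---|---|
| 0 / 0 | 60% vs 30% | 82% | 88% |
| 10% / 10% | 54% vs 27% | 75% | 80% |
| 25% / 25% | 45% vs 22.5% | 64% | 67% |
| 50% / 50% | 30% vs 15% | 42% | 44% |
| 50% / 25% | 30% vs 22.5% | 13% | 14% |
| 25% / 50% | 45% vs 15% | 90% | 92% |
| No true effect, 0 / 25% | 60% vs 45% | 28% false positives | 34% false positives |

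Equal clearance leaves the relative risk at 0.5 and shrinks the risk difference from 30 points to 27, 22.5 or 15, so its cost is power. Unequal clearance distorts the estimate: 50% / 25% cuts the difference from 30 points to 7.5, and 0 / 25% under no effect produces a difference of 15 points. The 45-per-arm column matches the number the plan expects to evaluate.

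**The case against.** **The ESQ may not be the source of the 0 h outcome.** A reader might infer that a patient rescued before the questionnaire is recorded as pain-free. The documents do not say so. They never state that the ESQ supplies the 0 h pain status, they describe it as covering symptoms other than pain, and its recall period is not shown. Subjective pain scores are also a named primary measure, and 7.2 plans a rank comparison of postoperative pain at 0 h. In the magnesium arm the analgesic depends on a numeric score, so a reading before rescue should exist there. This stands, and it limits the claim to events that can be missed. It does not close the gap: no such score is tied to 0 h, and none is written into the control-arm text.

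**The direction is open.** A reader might also infer that control patients are rescued more, as the trial's hypothesis predicts, so that the bias can only hide a benefit. The hypothesis predicts less pain and lower opioid requirements with magnesium. Both would follow from fewer painful patients, with the same share of them rescued in each arm. The written text could even point the other way, since it lists analgesia for every score from 1 upwards in the magnesium arm only. Nor do the documents show that recovery time differs by arm.

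**The size is assumed.** Section 7.1 does not say when the institutional 60% was measured. If it was recorded after routine treatment, some masking is already in it and the illustration counts it twice. At the full 50 per arm, 10% equal clearance still leaves 80% power. Both points stand.

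**Conclusion.** The gap holds on the text: an undefined 0 h, one scheduled PACU self-report timed by nursing judgement, analgesia available before it in both arms, and no rule for pain treated beforehand. A site that follows the plan exactly can miss events.

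The documents support no single figure for the consequence. Every row with clearance above zero rests on an assumed share, on 60% vs 30% (or 60% in both arms) as the true incidence before treatment, and on the cleared events being scored as absent. On those assumptions, even 10% equal clearance takes power at 45 per arm below the planned 80%, and unequal clearance can conceal a true effect or produce a false one. It should be settled before enrolment, because a reading not taken before rescue cannot be recreated.

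**What to change.** Amend 6.3 and 7.2 as follows.

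- Define the 0 h outcome as the first numeric pain rating, with the site of pain, that the patient can give in the PACU before any PACU analgesic. State the score that counts as pain present.
- Take it the same way in both arms, by staff unaware of allocation where possible. Section 5.8 covers only the endoscopist and the patient.
- Record the clock times of extubation, rating and first PACU analgesic.
- Prespecify that esophageal or retrosternal pain treated before a rating is possible counts as an event, and add a sensitivity analysis in which it does not.
- Keep the later ESQ as a symptom measure.
- State in 7.1 when the 60% was measured relative to treatment.

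The cost is one amendment and a few case report form fields: the rating, the site and three times. Scoring is already implied in the magnesium arm and would have to be written in for control. The downside is that a few events would rest on the rescue record. That record could differ by arm for reasons other than pain, because the PACU rescue text in 6.2.2.2 and 6.2.2.3 differs and the blinding of PACU staff is not stated. Those two sections must be reconciled. No rescue rule is proposed here.
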